## **7 STATISTICAL ANALYSES**

### **7.1 General Methods**

Unless otherwise noted, the following subsections describe tabulations of discrete variables, by the frequency and proportion of subjects falling into each category, grouped by treatment (with total). Percentages given in these tables will be rounded and, therefore, may not always sum to 100%. Continuous variables will be summarized by treatment group (with total) using the mean, standard deviation, median, minimum and maximum values. If a missing category is not being presented in the data display, only those subjects with non-missing values for the parameter being assessed are included in the percentage calculation.

Time to event distribution will be estimated using Kaplan Meier techniques. This will be done for endpoints progression free survival, overall survival and duration of response (note that TTR will be analyzed using summary statistics such as mean, SD, median, min, max). Median survival time along with 95% CI will be constructed based on a log-log transformed CI for the survivor function  $S(t)$ . Rates at fixed time points will be derived from the Kaplan Meier estimate and corresponding confidence interval will be derived based on Greenwood formula for variance derivation and on log-log transformation applied on the survivor function  $S(t)$ .

Confidence intervals for binomial proportions will be derived using the Clopper-Pearson method.

Formal hypothesis testing with control of Type I error will not be conducted for any of the endpoints in this study. No p-values will be presented. Confidence intervals, when presented, will be for descriptive purposes only and will not be adjusted for multiplicity.

Unless otherwise noted, safety analyses will be performed using the on-treatment definition for the entire study treatment period (i.e. combined Part 1 and Part 2 treatment periods) as defined in [Section 6.1.2](#). Alternate analysis periods will be used for specific endpoints or selected analyses as described in the corresponding endpoint or analysis section of this SAP.

Please see the following sections for additional details:

### **7.2 Study Conduct**

#### **7.2.1 Accrual**

The accrual pattern will be summarized per country, investigational site, and per month for all randomized subjects. Randomization date (if applicable), first dosing date, country, investigational site will be presented in a by subject listing of accrual.

Furthermore, the accrual pattern will be summarized by the stratification factor IMDC prognostic score.

#### **7.2.2 Relevant Protocol Deviations**

The following programmable deviations will be considered as relevant protocol deviations and summarized by treatment group and overall. Non-programmable relevant eligibility and on

treatment protocol deviations, as well as significant (both programmable and non programmable) eligibility and on-treatment protocol deviations will be reported through ClinSIGHT listings.

At Entrance:

- Subjects with baseline KPS < 70%
- Subjects who received prior systemic anti-cancer treatment in the metastatic setting
- Subjects without histologically confirmed RCC with a clear-cell component, documented advanced or metastatic (AJCC Stage IV) RCC

On-study:

- Subjects receiving anti-cancer therapy (chemotherapy, hormonal therapy, immunotherapy, standard or investigational agents for treatment of cancer) while on study therapy
- Subjects treated differently than as randomized (subjects who received the wrong treatment, excluding the never treated)

Listings will also be provided.

### **7.3 Study Population**

Summaries of study population will be based on all treated subjects, except that of subject disposition which will be based on all enrolled subjects.

#### **7.3.1 Subject Disposition**

The total number of subjects enrolled (randomized or not randomized) will be presented along with the reason for not being randomized. This analysis will be performed on the all enrolled population only.

Number of subjects who discontinued study treatment

- during Part 1 for All Treated Subjects,
- during the overall study for All Treated Subjects, and
- during Part 2 for All Subjects Treated in Part 2,

along with corresponding reason for discontinuation will be tabulated by treatment group as treated. Reason for discontinuation will be derived from subject status CRF page.

Number of subjects randomized but not treated along with the reason will be tabulated by treatment group as randomized. This analysis will be performed on the all randomized population only.

A subject listing for all randomized subjects will be provided showing the subject's randomization date (if applicable), first and last dosing date, off study date and reason for going off-study. A subject listing for subjects not randomized will also be provided, showing the subject's race, gender, age, consent date and reason for not being randomized.

### **7.3.2 Demographics and Baseline Characteristics**

The following baseline characteristics will be summarized by treatment group, for the population of All Treated Subjects. All baseline presentations will identify subjects with missing measurements. Listings will also be provided.

- Age (descriptive statistics)
  - Age category (< 65, ≥ 65- < 75, ≥ 75)
  - Gender (male, female)
  - Race (White, Black or African American, Asian, Other)
  - Ethnicity (Hispanic/Latino and Not Hispanic/Latino)
  - Region (US, Australia, Chile; per IVRS)
  - Karnofsky performance status (100, 90, 80, 70, <70)
  - IMDC prognostic score (0, 1-2, ≥ 3) (source: CRF)
  - Weight (descriptive statistics)
  - PD-L1 expression summary (0-1%; 1-5%; 5-10%; 10%)
  - Hemoglobin (<LLN, ≥ LLN)
  - Alkaline phosphatase (< ULN, ≥ ULN)
  - LDH level (≤ 1.5 x ULN, >1.5 x ULN)
  - Corrected Calcium (≤ 10 mg/dl, >10mg/dl)
  - History of Brain Metastases (Yes, No)
  - Time from initial disease diagnosis to randomization (<1 year, ≥1 year)
  - All lesions (Investigator Tumor Assessments at Baseline): sites of disease, number of disease sites per subject.
  - Target lesions (Investigator Tumor Assessments at Baseline): Presence of target lesions, site of target lesion, sum of longest diameter of target lesion.
- Similarly the following IVRS data will be summarized by treatment group as randomized.
- IMDC prognostic score (0, 1-2, ≥ 3)

### **7.3.3 Medical History**

General medical history will be listed by subject.

### **7.3.4 Prior Therapy**

- Prior adjuvant or neo-adjuvant therapy agents for completely resectable RCC will be summarized by treatment group for All Treated Subjects..

### **7.3.5 Baseline Examinations**

Subjects with abnormal baseline physical examination will be tabulated by examination criteria and by treatment group for All Treated Subjects.

### **7.3.6 Discrepancies between IVRS and CRF information**

Summary tables (cross-tabulations) of the stratification factor for All Treated Subjects by treatment group will be provided to show any discrepancies between what was reported through IRT vs. CRF data.

- IMDC prognostic score (0, 1-2,  $\geq 3$ ) (IRT vs. CRF data)

## **7.4 Extent of Exposure**

Analyses will be performed by treatment group “as treated” in all treated subjects, unless otherwise specified.

### **7.4.1 Administration of Study Therapy**

The following parameters will be summarized (descriptive statistics) by treatment group:

- Time from randomization to first dose of study therapy (0 to 3 days, > 3 to 7, > 7 to 14, > 14 to 21, > 21 to 28, > 28)
- Number of concomitant doses received (nivolumab + ipilimumab) and number of nivolumab flat doses received.
  - For Arm B a subject will be considered to have received concomitant doses of nivolumab and ipilimumab if both infusions are administered on the same date.
  - For Arm A a subject will be considered to have received concomitant doses of nivolumab and ipilimumab if any FRC infusion was administered.

The following parameters will be summarized (descriptive statistics) by treatment group and study therapy (nivolumab and ipilimumab for Arm B, BMS-986237 for Arm A).during Part 1 for All Treated Subjects:

- Number of doses received
- Cumulative dose in mg/kg
- Relative dose intensity (%) using the following categories: < 50%; 50 - < 70%; 70 - < 90%; 90 - < 110%;  $\geq 110\%$
- Infusion duration in minutes

In addition, the same set of parameters will be summarized (descriptive statistics) for nivolumab flat dosing during Part 2 for All Subjects Treated in Part 2:

Duration of treatment will be presented by treatment group using a Kaplan-Meier curve whereby the last dose date will be the event date for those subjects who are off study therapy. Median duration of treatment and associated 95% CI will be provided. Subjects who are still on study therapy will be censored on their last dose date. Duration of study therapy will also be summarized

in a table with descriptive statistics (mean, minimum, and maximum). The percentage of subjects with study therapy duration > 3 months, > 6 months, > 9 months, and > 12 months will be tabulated.

A by-subject listing of dosing of study medication (record of study medication, infusion details, and dose changes) and a listing of batch numbers will be also provided.

**Table 7.4.1-1: Study Therapy Parameter Definitions During Part 1 (Combination Portion)**

	BMS-986237 (Co-administration FRC)	Nivolumab (Arm B)	Ipilimumab (Arm B)
Dosing Schedule per Protocol	4 mg/kg every 3 weeks for 4 doses	3 mg/kg every 3 weeks for 4 doses	1 mg/kg every 3 weeks for 4 doses
Dose	Dose (mg/kg) is defined as Total Dose administered (mg)/Most recent weight (kg). Dose administered in mg at each dosing date and weight are collected on the CRF.	Dose (mg/kg) is defined as Total Dose administered (mg)/Most recent weight (kg). Dose administered in mg at each dosing date and weight are collected on the CRF.	Dose (mg/kg) is defined as Total Dose administered (mg)/Most recent weight (kg). Dose administered in mg at each dosing date and weight are collected on the CRF.
Cumulative Dose	Cum Dose (mg/kg) is the sum of the doses administered to a subject during Part 1.	Cum Dose (mg/kg) is the sum of the doses administered to a subject during Part 1.	Cum Dose (mg/kg) is the sum of the doses administered to a subject during Part 1.
Relative Dose Intensity (%)	$\text{Cum dose} / [(\text{Last Part 1 dose date} - \text{Start dose date} + 21) \times 4/21] \times 100$	$\text{Cum dose} / [(\text{Last Part 1 dose date} - \text{Start dose date} + 21) \times 3/21] \times 100$	$\text{Cum dose} / [(\text{Last Part 1 dose date} - \text{Start dose date} + 21) \times 1/21] \times 100$
Infusion Duration (mins)	Each infusion duration is calculated as infusion stop date/time - infusion start date/time.	Each infusion duration is calculated as infusion stop date/time - infusion start date/time.	Each infusion duration is calculated as infusion stop date/time - infusion start date/time.
Duration of Treatment	Last Part 1 dose date - Start dose date + 1	Last Part 1 dose date - Start dose date + 1	Last Part 1 dose date - Start dose date + 1

**Table 7.4.1-2: Study Therapy Parameter Definitions During Part 2 (Maintenance)**

	Nivolumab (Arms A and B)
Dosing Schedule per Protocol	480 mg flat dose every 4 weeks
Dose	Dose (mg) = total dose delivered as recorded on Record of Study Medication CRF
Cumulative Dose	Cum Dose (mg) is the sum of the doses administered to a subject during Part 2.
Relative Dose Intensity (%)	$[\text{Cum dose (mg)} / ((\text{Last dose date in Part 2} - \text{First dose date in Part 2} + 28) \times 480/28)] \times 100$
Infusion Duration (mins)	Each infusion duration is calculated as infusion stop date/time - infusion start date/time.
Duration of Treatment	last dose date in Part 2- first dose date in Part 2 + 1

## **7.4.2 Modifications of Study Therapy**

### **7.4.2.1 Dose Delays**

Each nivolumab, ipilimumab, or BMS-986237 infusion may be delayed. A dose will be considered as actually delayed if the delay is exceeding 3 days (ie greater than or equal to 4 days from scheduled dosing date). All studies drugs must be delayed until treatment can resume. Reason for dose delay will be retrieved from CRF dosing pages.

The following parameters will be summarized by treatment group:

- Number of dose delays per subject, length of delay, and reason for delay

### **7.4.2.2 Infusion Interruptions and Rate Changes**

Each nivolumab, ipilimumab, or BMS-986237 infusion can be interrupted and/or the IV infusion rate can be reduced. This information will be retrieved from CRF dosing pages.

The following parameters will be summarized by treatment group:

- Number of subjects with at least one dose infusion interruption, the reason for interruption, and the number of infusion interruptions per subject.
- Number of subjects with at least one IV infusion rate reduction and the reason for reduction.

### **7.4.2.3 Dose Escalations**

Dose escalations are not permitted for any study drug.

### **7.4.2.4 Dose Reductions**

Dose reductions are not permitted for any study drug.

### **7.4.2.5 Dose Omissions**

Dose omissions are not permitted for any study drug.

[REDACTED]

## 7.5 Efficacy

The primary endpoint is related to safety and there are no primary efficacy endpoints. Analysis methods for the primary safety endpoint are described in [Section 7.6.1](#). Descriptive analyses of secondary and exploratory efficacy endpoints will be performed and are described below.

### 7.5.1 Objective Response Rate

ORRs (based on investigator assessments using RECIST 1.1 criteria) and corresponding 95% exact CIs will be calculated using the Clopper Pearson method for each of the treatment arms. BOR will be tabulated for each treatment group. Associated odds ratios and 95% CIs for Arm A relative to Arm B will be calculated using Cochran-Mantel-Haenszel (CMH) methodology, adjusting for the stratification factor IMDC prognostic score (IVRS source). An estimate of the difference in ORRs and corresponding 2-sided 95% CI will be calculated using CMH methodology, adjusting for the same stratification factor as above.

Subgroup Analysis (Arms A and B only): To assess consistency of treatment effects in ORR in different subsets, a “forest” plot of the unweighted differences in ORRs and corresponding exact 95% CIs using the Newcombe method will be produced for the following variables:

- IMDC prognostic score (0, 1-2,  $\geq 3$ ) (source: clinical database)
- Age category (< 65,  $\geq 65$ - < 75, and  $\geq 75$ )
- Gender (male and female)
- Race (white, black, asian, and other)
- Region (US, Chile, Australia)
- Karnofsky performance status (< 90 vs.  $\geq 90$ )
- History of Brain Metastases (Yes and No)
- Time from initial disease diagnosis to randomization (<1 year,  $\geq 1$  year)
- LDH level ( $\leq 1.5$  x ULN,  $>1.5$  x ULN)
- Hemoglobin (<LLN,  $\geq$  LLN)
- Corrected Calcium ( $\leq 10$  mg/dl,  $>10$ mg/dl )
- Alkaline phosphatase (< ULN,  $\geq$  ULN)
- Baseline PD-L1+ status based on a 1% cut off
- Baseline PD-L1+ status based on a 5% cut off
- Baseline PD-L1+ status based on a 10% cut off

If a subgroup category has less than 10 subjects per treatment group, ORR will not be computed/displayed.

Duration of Objective Response (DOR): DOR curves in each treatment group will be estimated using the KM product-limit method for subjects with a BOR of CR or PR. Median DOR, corresponding two-sided 95% CI, and range will be reported.

Time to Objective Response: Summary statistics of TTR will be provided by treatment group for subjects with a BOR of CR or PR. TTR curves will be estimated using the KM product-limit method in all treated subjects and will represent the cumulative rate of response over time. For non-responders, subjects will be censored at the maximum time of response + 1 day of all subjects in their respective treatment group. Cumulative response rates will be tabulated at Week 12 and Month 6.

Other Analyses: The following subject-level graphics will be provided by treatment group.

- For responders only, the time course of the following events of interest will be graphically displayed: tumor response, tumor progression, last dose received, and death.
- For response-evaluable subjects (treated subjects with baseline and at least one on-study tumor assessment), a waterfall plot showing the best reduction in target lesion tumor burden based on investigator assessment.

### **7.5.2 Progression Free Survival**

PFS curves for each treatment group will be estimated using the Kaplan-Meier (KM) product limit method in All Treated Subjects. Median PFS and corresponding two-sided, 95% confidence intervals will be computed. Descriptive HRs and corresponding two sided 95% CIs for Arm A relative to Arm B will be estimated using a Cox proportional hazards model, with treatment group as a single covariate, stratified by IMDC prognostic score at screening (IVRS source). PFS rates at 6 months with 95% CIs will be estimated using KM methodology.

The source of progression event (death versus progression) will be summarized by treatment group.

The status of subjects who are censored in the PFS KM analysis will be tabulated for each treatment group using the following categories:

- On-study (on-treatment, in follow-up)
- Off-study (lost to follow-up, withdrawn consent, never treated)
- Received subsequent anticancer therapy

[REDACTED]

Survival rates at 6 months will be estimated using KM estimates on the OS curve for each treatment group. Associated two-sided 95% CIs will be calculated.

#### **7.5.4 Subject Follow-Up**

The extent of follow-up defined as the time between randomization date and last known date alive (for subjects who are alive) or death date (for subjects who died) will be summarized descriptively (median, min, max) for all treated subjects in Arms A and B.

The currentness of follow-up, defined as the time between last OS contact (ie, last known date alive or death date) and data cut-off date, will be summarized by treatment group. Subjects who died before data cut-off date will automatically have zero value for currentness of follow-up. For subjects with last known date alive after data cut-off date, they will have zero value for currentness of follow-up as well. The currentness of follow-up will be categorized into the following categories: 0 days, 1-30 days, 31-60 days, 61-90 days, 91-120 days, 121-150 days, 151 or more days.

#### **7.5.5 Interim Analysis**

Not applicable.

### **7.6 Safety**

#### **7.6.1 MedDRA Anaphylactic Reaction Broad Scope SMQ AE Incidence Rate**

For purposes of the primary endpoint analysis, the incidence rate of AEs in the Broad Scope MedDRA Anaphylactic Reaction SMQ occurring within 2 days after any dose in the Part 1 dosing period will be reported by treatment arm for all treated subjects. Corresponding 95% CIs for the rate in each treatment arm will be calculated using the Clopper-Pearson method. An estimate and confidence interval for the difference in rates between treatment arms will be presented based on CMH method of weighting, adjusting for IMDC prognostic score at screening.

Additional characterization of the events meeting the primary endpoint criteria will be provided, including summaries by system organ class (SOC) and preferred term (PT). Adverse events will be coded using the Medical Dictionary for Regulatory Activities (MedDRA), and the most recent version of the dictionary at the time of the database lock will be used. Adverse events results will be graded for severity using NCI Common Terminology Criteria for Adverse Events (CTCAE) Version 4.0 criteria. In the AE summary tables subjects will be counted by worst CTC grade only once at the Preferred Term (PT), only once at the System Organ Class (SOC), and only once at subject level for the counting of total number of subjects with an AE.

### **7.6.2 MedDRA Anaphylactic Reaction Narrow Scope SMQ AE Incidence Rate**

The incidence rate of Anaphylactic reactions based on MedDRA narrow scope SMQ by treatment arm, the difference in rates between arms, and the corresponding 95% confidence intervals will be reported using the same methods as described above for the primary endpoint analysis. Summaries by worst CTC grade, SOC, and PT will also be provided similar to the primary endpoint.

### **7.6.3 Drug-related and All Causality Grade 3-5 AEs Incidence Rates**

Analyses of drug-related and all causality Grade 3-5 AEs will be aligned with the Core Safety SAP as described in Section 7.6.8.

### **7.6.4 Deaths**

See Core Safety SAP.

### **7.6.5 Serious Adverse Events**

See Core Safety SAP.

### **7.6.6 Adverse Events Leading to Discontinuation of Study Therapy**

See Core Safety SAP.

### **7.6.7 Adverse Events Leading to Dose Modification**

See Core Safety SAP.

### **7.6.8 Adverse Events**

See Core Safety SAP. Summaries of AEs and drug-related AEs will also be provided separately for events with onset during the Part 1 treatment period for All Treated Subjects and for events with onset during the Part 2 treatment period for All Subjects Treated in Part 2. These additional summaries by treatment period will be performed using the 30-day safety window only.

### **7.6.9 Select Adverse Events**

See Core Safety SAP.

### **7.6.10 Immune Modulating Medication**

See Core Safety SAP.

### **7.6.11 Multiple Events**

See Core Safety SAP.

### **7.6.12 Other Events of Special Interest**

See Core Safety SAP.

### **7.6.13 Immune-Mediated Adverse Events**

See Core Safety SAP.

### **7.6.14 Laboratory Parameters**

See Core Safety SAP. Lipase and Amylase will be added to the list of lab parameters to be summarized.

### **7.6.15 Vital Signs and Pulse Oximetry**

See Core Safety SAP.

### **7.6.16 Immunogenicity Analysis**

See Core Safety SAP.

### **7.6.17 Pregnancy**

See Core Safety SAP.

### **7.6.18 Adverse Events By Subgroup**

See Core Safety SAP. Categories for region will be the same as those specified in [Section 7.5.1](#)

## **7.7 Pharmacokinetics**

For purposes of the secondary endpoint, PK comparisons will be summarized using descriptive summary statistics to compare nivolumab and ipilimumab predose and end of infusion (EOI) concentrations administered as FRC to that of sequentially administered nivolumab and ipilimumab. End of infusion and trough (predose) concentration levels of nivolumab and ipilimumab will be summarized by treatment arm and study day using descriptive statistics (N, mean, SD, geometric mean, %CV, median, minimum, and maximum). ). Graphs of geometric mean trough concentrations of nivolumab and ipilimumab, and also the geometric mean End of Infusion (EOI) concentrations of nivolumab and ipilimumab vs. study day by treatment arm will be provided for visual comparison of FRC vs. sequential administration of nivolumab and ipilimumab.

The nivolumab and ipilimumab concentration vs time data obtained in this study may be combined with data from other studies in the clinical development program to develop a population PK model, if needed, to compare model based PK parameters and exposure following administration of the FRC and sequential administration. This model will be used to determine measures of individual exposure (such as single dose and steady state peak, trough and timeaveraged concentrations). If conducted, the results of the population PK analyses will be reported separately.

[REDACTED]

[REDACTED]

[REDACTED]

[REDACTED]

[REDACTED]

[REDACTED]

[REDACTED]

[REDACTED]

[REDACTED]

[REDACTED]

[REDACTED]

[REDACTED]

[REDACTED]

[REDACTED]

[REDACTED]

[REDACTED]

[REDACTED]

[REDACTED]

[REDACTED]

[REDACTED]

[REDACTED]

[REDACTED]

[REDACTED]

[REDACTED]

[REDACTED]

[REDACTED]

[REDACTED]

[REDACTED]

[REDACTED]

[REDACTED]

[REDACTED]

[REDACTED]

[REDACTED]

[REDACTED]

[REDACTED]

[REDACTED]

[REDACTED]

A by-subject listing of these biomarkers measures will be provided.

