10.3.2.1 Pharmacokinetic Analyses as a Secondary Endpoint

One of the secondary endpoint is to get PK comparisons of nivolumab and ipilimumab administered as FRC to that of sequentially administered nivolumab and ipilimumab. PK will be measured using serum concentration-time data.

PK comparisons will be summarized using descriptive summary statistics to compare nivolumab and ipilimumab predose and EOI concentrations administered as FRC to that of sequentially administered nivolumab and ipilimumab.

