#### **4.2.4 Pharmacokinetic Analyses**

The fourth secondary endpoint is PK comparisons of nivolumab and ipilimumab administered as FRC to that of sequentially administered nivolumab and ipilimumab. PK will be measured using serum concentration-time data.

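### The PK comparison of FRC with sequential dosing is a secondary endpoint, but the plan pre-specifies no between-arm estimate with its uncertainty

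*SAP*

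**What the plan says.** SAP 4.2.4 defines the endpoint as a comparison between arms: "The fourth secondary endpoint is PK comparisons of nivolumab and ipilimumab administered as FRC to that of sequentially administered nivolumab and ipilimumab". Protocol Table 4-1 defines it the same way.

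The method is in SAP 7.7: "PK comparisons will be summarized using descriptive summary statistics to compare nivolumab and ipilimumab predose and end of infusion (EOI) concentrations". End-of-infusion (EOI) and predose concentrations are to be "summarized by treatment arm and study day using descriptive statistics (N, mean, SD, geometric mean, %CV, median, minimum, and maximum"). Graphs of geometric means by arm "will be provided for visual comparison of FRC vs. sequential administration of nivolumab and ipilimumab". Protocol 10.3.2.1 is shorter: "PK comparisons will be summarized using descriptive summary statistics to compare nivolumab and ipilimumab predose and EOI concentrations administered as FRC", set against sequential dosing.

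SAP 7.7 and Protocol 10.3.2.2 also mention a model-based route. The data "may be combined with data from other studies in the clinical development program to develop a population PK model, if needed", and "If conducted, the results of the population PK analyses will be reported separately". No contrast or interval is specified for that model.

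SAP 7.1 excludes hypothesis tests and p-values but allows confidence intervals as descriptive statistics. Protocol Table 9.5-1 schedules samples for both drugs at Cycle 1, 2 and 4 EOI and at Cycle 1, 2, 4 and 5 predose.

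**The concern.** The endpoint asks how exposure in one arm relates to exposure in the other. The planned output describes each arm and leaves the relation to be judged by eye from two geometric means and a plot.

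A reader of the study report could not then tell whether a visible gap is more than sampling variation, or how large a difference an apparent match leaves open. The second matters more here, because the research hypothesis in the SAP is one of no clinically relevant difference, although that hypothesis concerns safety. When similar exposure is the expected finding, the interval carries most of the information.

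The plan takes this view elsewhere. SAP section 5 justifies the sample size by the width of a between-arm interval for the primary endpoint, with no test.

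**Working it through.** **1. What each endpoint gets in the visible text**

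| Endpoint | Between-arm estimate | Interval | Source |
|---|---|---|---|
| Broad-scope SMQ (primary) | rate difference, CMH weights | yes | SAP 7.6.1 |
| Narrow-scope SMQ | rate difference, same method | yes | SAP 7.6.2 |
| Drug-related Grade 3-5 AEs | none stated | none stated | Protocol 10.3.2; SAP 7.6.3 |
| All-causality Grade 3-5 AEs | none stated | none stated | Protocol 10.3.2; SAP 7.6.3 |
| PK comparison | none | none | SAP 7.7; Protocol 10.3.2.1 |
| ORR | difference and odds ratio | yes | SAP 7.5.1 |
| PFS | hazard ratio | yes | SAP 7.5.2 |

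The Grade 3-5 analyses are referred to a Core Safety SAP that is not among the documents. Those endpoints are defined as rates; the PK endpoint is defined as a comparison.

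**2. The plan's own precision figure**

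The documents state no PK precision. The figure they do state, for the primary endpoint at 24% in each arm with 50 per arm, is reproduced by a Wald interval:

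1.96 × √(0.24 × 0.76/50 + 0.24 × 0.76/50) = 1.96 × 0.0854 = 0.167, that is (-16.7%, 16.7%), as in SAP Table 5-1. The other four rows of that table also reproduce.

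**3. What the same participants would give for PK**

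Inputs:
- 50 treated per arm is the target (SAP section 5). The PK population is treated participants with concentration data (SAP 6.3), so 50 is the planned maximum per arm. The cases of 40 and 25 per arm are assumptions.
- The between-participant CV is **not in the documents**. It is assumed at 25%, 40% and 60%.
- Log-normal concentrations, one value per participant at a given time point, no stratification.

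Formulas: SD of log concentration s = √ln(1 + CV²); standard error of the log ratio = s × √(2/n); CI factor = exp(t × SE), with 2n − 2 degrees of freedom. The limits are the observed ratio divided by and multiplied by the factor.

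Worked case, CV 40% and n = 50: s = √ln(1.16) = 0.385; SE = 0.385 × √(2/50) = 0.0771. With t = 1.661 (90%), the factor is exp(0.128) = 1.14. With t = 1.984 (95%), it is exp(0.153) = 1.17.

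| Evaluable per arm | Level | CV 25% | CV 40% | CV 60% |
|---|---|---|---|---|
| 50 | 90% | 1.09 | 1.14 | 1.20 |
| 50 | 95% | 1.10 | 1.17 | 1.25 |
| 40 | 90% | 1.10 | 1.15 | 1.23 |
| 40 | 95% | 1.12 | 1.19 | 1.28 |
| 25 | 90% | 1.12 | 1.20 | 1.30 |
| 25 | 95% | 1.15 | 1.25 | 1.37 |

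For an observed ratio of 1, 50 per arm and CV 40%, the 95% interval would be 0.86 to 1.17.

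**4. Which time points support a clean contrast**

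- *Staying on treatment.* Under footnote b of Protocol Table 9.5-1, participants who discontinue move to follow-up sampling. Cycle 4 and 5 values therefore come only from those still on treatment, in unknown number. Cycle 1 EOI and Cycle 2 predose are least affected.
- *Infusion length.* In the same table, the ipilimumab EOI sample falls at the end of a 60-minute infusion in Arm A and a 30-minute infusion in Arm B. That ratio mixes infusion length with co-formulation. The nivolumab infusion lasts 60 minutes in both arms, and predose values avoid most of the problem.

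**The case against.** The strongest reply is that the protocol and SAP agree, the whole study is descriptive, PK ranks fourth among the secondary endpoints, and no similarity margin exists for an interval to serve. With only predose and EOI samples, a population model is a natural route to exposure, and both documents name it. The by-arm tables also let a reader divide one geometric mean by the other and approximate an interval from N and %CV.

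Part of this stands. A reader might infer that the plan makes no comparison at all; it does not support that, because side-by-side summaries and graphs are planned. A reader might infer that PK is the only secondary endpoint without an interval; the Grade 3-5 AE rates have none in the visible text either. A reader might also infer that an equivalence test is missing; the documents set no PK margin and exclude formal testing, so none is called for. Nor can it be said that the data will certainly give a tight answer, since the CV and the evaluable numbers are unknown.

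The rest does not stand. SAP 7.1 allows descriptive intervals, and the plan uses them for four other between-arm contrasts. The population model may never be run, would pool other studies, and would be reported elsewhere. A home-made interval is no pre-specified result, and the SAP does not say whether %CV is arithmetic or geometric. The redacted block after SAP 7.7 is unlikely to hold a contrast: the SAP contents list shows no PK subsection before 7.8, and the visible text of Protocol 10.3.2.1 has none.

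**Conclusion.** The concern holds in this form: a secondary endpoint defined as a comparison has no pre-specified between-arm estimate and no statement of uncertainty, although the plan supplies both for its primary endpoint, narrow-scope SMQ, ORR and PFS. The absence is a matter of text and is certain for the visible documents.

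The size of what is lost is conditional. If 50 per arm are evaluable and the CV lies between 25% and 60%, the 95% CI factor is about 1.10 to 1.25. If only 25 per arm remain at the later cycles, it is about 1.15 to 1.37. Both CV and attrition are assumptions. The point is moderate: it concerns a secondary endpoint and leaves the sample size, data collection and primary analysis untouched.

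**What to change.** In SAP 7.7 add the following, with a matching sentence in Protocol 10.3.2.1:

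- For each analyte, report the geometric mean ratio (Arm A/Arm B) with a descriptive confidence interval from log-transformed concentrations, at Cycle 1, 2 and 4 EOI and at Cycle 2, 4 and 5 predose. No test.
- State the level: 95% to match the plan's other intervals, or 90% if the SAP says so. Adjustment for IMDC score is optional.
- Give most weight to Cycle 1 EOI and Cycle 2 predose. For ipilimumab, Cycle 2 predose is the cleaner of the two.
- Footnote that Cycle 4 and 5 ratios are conditional on remaining on treatment, and that ipilimumab EOI ratios also reflect the 60-minute versus 30-minute infusion.
- Show the number of evaluable participants per arm beside each ratio, and say whether %CV is arithmetic or geometric.

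The cost is one SAP paragraph, one protocol sentence and one table, with no added participants or samples. The population PK model can stay optional.
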